## 4. PLANNED ANALYSES

The following formal analyses will be performed for this study:

- Day 7 DMC.
- Day 84 DMC.
- Primary analysis.
- Final analysis.

### 4.1. DATA MONITORING COMMITTEE (DMC)

The DMC safety reviews, based on a separate statistical analysis plan (SAP) and set of TLF shells (as provided by Aeras), have been completed at two time points:

- Day 7 DMC:
  - o For the Safety and Immunogenicity Cohort once the last participant reached Day 7, the DMC reviewed unblinded safety data.
- Day 84 DMC:
  - o For the Safety and Immunogenicity Cohort once the last participant reached Day 84, the DMC reviewed unblinded safety data.

The DMC made a formal recommendation about the continued conduct of the trial after each safety review. Enrollment continued while the reviews were being conducted.

### 4.2. PRIMARY ANALYSIS

The primary analysis, based on a separate SAP and set of TLF shells was completed once the following two conditions were met:

- At least 64 primary endpoints had accrued (refer to Section 14.1.1: Primary Efficacy Endpoint for a description of the primary endpoints).
- The median follow-up time (for all participants in the Modified Intent-to-treat [mITT] analysis set) from Day 0 was at least 15 months.

The DMC received the primary analysis report and provided a recommendation to the study sponsor regarding whether to continue, stop or modify the trial as currently planned.

---

Document: Aeras\_C-040-404\_SAP\_V2\_0  
Author: [name]

Version Number: 2.0  
Version Date: 29SEP2017

Template No: CS\_TP\_BS016 – Revision 3  
Effective Date: 01May2012

Reference: CS\_WI\_BS005

### 4.3. FINAL ANALYSIS

The final analysis identified in this SAP and relevant set of TLF shells will be performed by QuintilesIMS Bloemfontein, South Africa (QBLM) Biostatistics. The final analysis is planned following:

- Aeras’s authorization of the final version of the SAP and relevant set of TLF shells.
- Aeras’s authorization of the final analysis sets.
- Final database lock and unblinding.

The final analysis will be performed on a clean locked database:

- All outstanding data issues and queries resolved.
- All unresolvable data issues documented in a separate data handling report (DHR) document from Data Management.
- All coding of medications, medical conditions, physical examination abnormalities and adverse events (AEs) completed.
- All reconciliation of vendor data with electronic case report form (eCRF) data completed successfully.

## 5. ANALYSIS SETS

Aeras authorization of assigned analysis sets is required for the final analysis. Agreement and authorization of participants included/excluded from each analysis set will be obtained prior to the unblinding activities of the study.

In view of the final analysis, the following analysis sets will be defined:

### 5.1. RANDOMIZED ANALYSIS SET

The Randomized analysis set is defined as all participants who were randomized to either H4:IC31, Placebo or BCG regardless of whether they received a study vaccination.

A participant will be programmatically included in the Randomized analysis set if the participant has a randomization number in the clinical study database, as recorded on the System Enrollment eCRF.

For analyses and presentations based on Randomized analysis set, participants will be analyzed according to the treatment assigned regardless of the treatment received.

### 5.2. SAFETY ANALYSIS SET

The Safety analysis set is defined as all participants included in the Randomized analysis set who received at least one dose of study vaccination (H4:IC31, Placebo or BCG).

---

Document: Aeras\_C-040-404\_SAP\_V2\_0  
Author: [name]

Version Number: 2.0  
Version Date: 29SEP2017

Template No: CS\_TP\_BS016 – Revision 3  
Effective Date: 01May2012

Reference: CS\_WI\_BS005

A participant will be included in the Safety analysis set if the participant:

- Is included in the Randomized analysis set.
- AND
- Has at least one date of study vaccination in the database as recorded on the Exposure (Day 0) or Exposure (Day 56) eCRF.

For analyses and presentations based on the Safety analysis set, participants will be analyzed according to the treatment received regardless of the treatment allocated (that is 'as treated'):

- For all presentations, including by dose at onset presentations, participants who received a different treatment to that allocated, but the same consistent treatment for all relevant doses, analyze and present participants according to the treatment received (both overall and per dose at onset).
- Participants who received a different treatment to that allocated, but not the same consistent treatment for all relevant doses (mixed treatment regimen), will be analyzed as described below:
  - o For all presentations, with the exception of by dose at onset presentations, analyze and present participants according to the following vaccine hierarchy: H4:IC31 followed by BCG and then placebo.
  - o For all by dose at onset presentations, analyze participants according to the treatment received for each dose at onset; therefore, participants are analyzed and presented according to different treatments per the relevant doses.

The Safety analysis set will be used as the primary analysis set for all safety and immunogenicity analyses.

### 5.3. MODIFIED INTENT-TO-TREAT ANALYSIS SET

The Modified Intent-to-treat analysis set is defined as all participants included in the Safety analysis set who had a negative QFT-GIT test result at Day 84.

A participant will be programmatically included in the Modified Intent-to-treat analysis set if the participant:

- Is included in the Safety analysis set.
- AND
- Has a negative QFT-GIT test result at the Day 84 visit.

For analyses and presentations based on the Modified Intent-to-treat analysis set, participants will be analyzed according to the treatment assigned regardless of the treatment received.

The Modified Intent-to-treat analysis set will be used for efficacy analyses.

## 5.5. PER PROTOCOL ANALYSIS SET

The Per Protocol analysis set is defined as all participants in the Modified Intent-to-treat analysis set who received all relevant doses of BCG, H4: IC31 or Placebo and had no major protocol deviations.

A participant will be included in the Per Protocol analysis set if the participant:

- Is included in the Modified Intent-to-treat analysis set.
- Received all relevant doses, based on the date of study vaccination as recorded on Exposure (Day 0) and Exposure (Day 56) eCRFs:
  - o BCG: Day 0.
  - o H4:IC31 or Placebo: Day 0 and Day 56.
- Did not have any major protocol deviations as recorded on the Protocol Deviation eCRF and agreed with Aeras prior to the relevant unblinding activities of the analysis/study.
- Did not have a treatment deviation as identified in collaboration with the clinical trial manager (CTM) in accordance with the Aeras/QuintilesIMS Process Instruction Treatment Deviation Identification and Authorization document.
- Out-of-window QFT-GIT positive results should not be included in the analysis for the PP analysis set.

Refer to the relevant Blind Data Review (BDR) documentation for additional details.

Document: Aeras\_C-040-404\_SAP\_V2\_0

Author: [name]

Version Number:

2.0

Version Date:

29SEP2017

Template No: CS\_TP\_BS016 – Revision 3

Reference: CS\_WI\_BS005

Effective Date: 01May2012

Copyright © 2012 Quintiles Transnational Corp. All rights reserved.

The contents of this document are confidential and proprietary to Quintiles Transnational Corp. Unauthorized use, disclosure or reproduction is strictly prohibited.

The Per Protocol analysis set will be based on the participant level flag assigned in Appendix 1 of the BDR report, as authorized by Aeras prior to DB lock.

Efficacy analyses will also be performed using the Per Protocol analysis set as a sensitivity analysis.

---

Document: Aeras\_C-040-404\_SAP\_V2\_0

Author: [name]

Version Number:

2.0

Version Date:

29SEP2017

Template No: CS\_TP\_BS016 – Revision 3

Reference: CS\_WI\_BS005

Effective Date: 01May2012

Copyright © 2012 Quintiles Transnational Corp. All rights reserved.

The contents of this document are confidential and proprietary to Quintiles Transnational Corp. Unauthorized use, disclosure or reproduction is strictly prohibited.

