### 6.1 Rules for Discontinuing Study Injections in an Individual Participant

Administration of additional study injections will be discontinued for an individual participant if he/she has any of the following:

- An objective clinical or laboratory parameter change which meets Grade 3 or Grade 4 severity, as defined in the protocol toxicity table, AND is judged to be possibly, probably, or definitely related to study injection\*
- Adverse event thought to be an allergic reaction to the study injection, including anaphylaxis or bronchospasm
- Any extensive rash (>40% body surface) on the thorax, abdomen, or limbs, including but not limited to urticaria, generalized petechiae, or erythema multiforme judged to be possibly, probably, or definitely related to study injection
- Development of active TB
- Development of autoimmune disease or immunosuppression, or an adverse event of special interest
- Receipt of investigational drug therapy or investigational vaccine (other than study injections received as part of this study)
- Any event that in the opinion of the principal investigator precludes administration of any further study injections
- Pregnancy

\*Excluding local injection site redness, induration, or ulceration that follow the normal expected course of BCG vaccination.

Subjects who are withdrawn from vaccination will be followed for a minimum of 6 months after the last study vaccination for safety.

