### 7.1 Subject Populations

The safety population will consist of all randomized subjects who received at least one dose of BCG or study vaccine (AERAS-404 or placebo).

The per-protocol population for efficacy analyses will consist of all randomized subjects who received all scheduled doses of BCG, AERAS-404, or placebo and had no major protocol deviations (to be described in the statistical analysis plan). The intent-to-treat population for efficacy and immunogenicity analyses will consist of all randomized subjects.

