#### 14.1.2. ANALYSIS OF PRIMARY EFFICACY ENDPOINT

The following tables will be presented for the Modified Intent-to-treat analysis set:

- QFT-GIT results at each visit:
  - o Number and percentage (%) of participants in each category per visit:
    - Negative.
    - Positive.
    - Missing.
  - o Percentage (%) of participants will be calculated relative to the total number of participants in the Modified Intent-to-treat analysis set who have QFT-GIT assessments available per treatment group per visit.

---

Document: Aeras\_C-040-404\_SAP\_V2\_0

Author: [name]

Version Number:

2.0

Version Date:

29SEP2017

Template No: CS\_TP\_BS016 – Revision 3

Reference: CS\_WI\_BS005

Effective Date: 01May2012

Copyright © 2012 Quintiles Transnational Corp. All rights reserved.

The contents of this document are confidential and proprietary to Quintiles Transnational Corp. Unauthorized use, disclosure or reproduction is strictly prohibited.

- Compliance to QFT-GIT testing:
  - o Number and percentage (%) of participants in each compliance category per visit:
    - Yes.
    - No.
    - Missing.
  - o Percentage (%) of participants will be calculated relative to the total number of participants in the Modified Intent-to-treat analysis set expected to have a QFT-GIT assessment available per treatment group per visit (N1).
- QFT-GIT conversion rates, primary endpoint (therefore endpoints occurring after Day 84):
  - o Number and percentage (%) of participants in each conversion status category:
    - Yes.
    - No.
    - Missing.
  - o Hazard ratio (H4:IC31/comparator) presented:
    - Point estimates (based on the Cox regression model).
    - P-values for the comparison of the estimated hazard ratios of QFT-GIT conversion based on a one-sided log-rank test.
      - H4:IC31 versus Placebo.
      - BCG versus Placebo.
      - H4:IC31 versus BCG (at the request of the sponsor's partner).
  - o Vaccine efficacy presented:
    - Point estimate (based on the hazard ratio estimates).
    - 80% two-sided CI based on the hazard ratio estimate from the Cox regression model.
  - o This table will be repeated for the Per Protocol, Adjusted Modified Intent-to-treat (First Recall Positive Omit) analysis sets. This table will also be repeated for the adjudication approach (refer to Section 3.3: Changes to Analysis from Protocol).

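### For BCG versus placebo, the Per Protocol dose rule can exclude placebo participants but in practice excludes no BCG participant

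*SAP*

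**What the plan says.** SAP 5.5 builds the PP set from the mITT set and adds a dose-completion rule by arm. BCG needs Day 0 only; the rule for the other arms is "H4:IC31 or Placebo: Day 0 and Day 56". This follows protocol 7.1, where the PP population is those who "received all scheduled doses of BCG, AERAS-404, or placebo and had no major protocol deviations".

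Two conditions are inherited in every arm. The Safety set (SAP 5.2) requires at least one study vaccination. The mITT set (SAP 5.3) adds a further criterion: "Has a negative QFT-GIT test result at the Day 84 visit".

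SAP 5.5 also lists filters that are not tied to an arm. One reads "Did not have any major protocol deviations as recorded on the Protocol Deviation eCRF". The others remove participants with treatment deviations and disregard QFT-positive results obtained out of window.

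On the role of the set, SAP 5.5 says: "Efficacy analyses will also be performed using the Per Protocol analysis set as a sensitivity analysis". SAP 14.1.2 says of the primary conversion table, which includes BCG versus placebo: "This table will be repeated for the Per Protocol, Adjusted Modified Intent-to-treat (First Recall Positive Omit) analysis sets". SAP 14.2.2 repeats the sustained-conversion tables on the PP set as well. Neither section gives a separate placebo rule for the BCG comparison.

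**The concern.** One placebo PP set serves both vaccine comparisons. Against H4:IC31 the two-dose rule is the same on both sides. Against BCG it is not.

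The second placebo injection is saline, so missing it cannot change a participant's risk of infection. In this comparison, dropping such a participant carries no information about adherence to an active product. It only selects on what happened after randomisation, such as attendance, illness or pregnancy. The dose rule makes no matching exclusion among BCG recipients, who have no Day 56 visit.

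What is at stake is how the PP result is read. If the mITT and PP estimates for BCG differ, part of the gap could come from this rule. Some placebo follow-up and events would also be left out of the PP comparison.

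**Working it through.** **1. Whom the dose rule can remove.** PP lies inside mITT, and mITT lies inside the Safety set, which requires at least one dose.

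- BCG: the regimen is one dose, so the Day 0 rule removes essentially nobody further.
- Placebo: the rule removes anyone who was Day 84 QFT-negative but had no second injection.

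**2. What governs the second injection.** Protocol 3.5 gives it only to those who have not met the stopping criteria in protocol 6.1, which opens: "Administration of additional study injections will be discontinued for an individual participant if he/she has any of the following". The list includes pregnancy, active TB and investigator judgement. Appendix A adds a pregnancy test and an eligibility re-check on Day 56. SAP 13.1 sets a window of study days 54 to 70, and SAP 13 records an out-of-window dose among its treatment-deviation variables. Table 3-1 shows no Day 56 visit for BCG. Whether a late injection alone leads to exclusion depends on a separate process document that SAP 5.5 cites.

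**3. The plan's own figure.** The documents give no figure for the PP set. The related figure is 80% power in protocol 7.6 (64 endpoints, 50% reduction, one-sided 10%). With one effective vaccine, the pair holds 64 × 1.5/2.5 = 38.4 events. Power = Φ(√38.4/2 × ln 2 − 1.282) = Φ(0.866) = 80.7%. The stated figure reproduces, and this point does not affect it.

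**4. Effect on the PP hazard ratio.** Let f be the share of mITT placebo participants without a valid second dose, and r their conversion hazard relative to the other placebo participants. Neither is in the documents. Assume the BCG arm holds the same mix of people and that the vaccine effect is the same in both groups. BCG keeps the full mix while placebo PP keeps only the completers, so

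HR_PP = HR × (1 − f + f·r), and VE_PP = 1 − HR_PP.

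At a true VE of 30% (HR 0.70; an illustrative value):

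| f | r = 0.5 | r = 1.5 | r = 2 |
|---|---|---|---|
| 3% | 31.05% | 28.95% | 27.90% |
| 5% | 31.75% | 28.25% | 26.50% |
| 10% | 33.50% | 26.50% | 23.00% |

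Example: f = 10%, r = 2 gives 0.70 × (0.90 + 0.20) = 0.77, so VE_PP = 23%. If the Day 56 rule is not applied to placebo in this comparison, the factor is 1.

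**5. Scale against sampling error.** Take 64 events (the trigger minimum), BCG VE of 30% and no H4:IC31 effect.

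- Placebo events: 64/2.7 = 23.7. BCG events: 23.7 × 0.7 = 16.6.
- SE(log HR) = √(1/23.7 + 1/16.6) = 0.32.
- 80% interval for VE: 1 − exp(−0.357 ± 1.282 × 0.32), or about -5.5% to 53.6%.
- The largest shift in the table, ln(1.10) = 0.095, is 0.3 SE. At f = 3% and r = 2, ln(1.03) = 0.030 is under 0.1 SE.

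**The case against.** The case for leaving the rule alone is substantial.

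- **Role.** PP is one sensitivity analysis among several. The SAP also plans interval-censored, recalled-tube and adjudicated analyses, and none is described as depending on the Day 56 dose. Efficacy rests on mITT, which has no such rule.
- **Shared filters.** Both arms must reach Day 84 with a negative test, which already removes early dropouts and early converters. Major-deviation exclusions reach BCG participants too.
- **Convention.** Requiring the full assigned regimen is the protocol's own definition, so the two documents agree.
- **Visibility.** SAP 13 tabulates by arm who received all vaccinations and who had the second in window, and SAP 9 records reasons for exclusion from each set.
- **Size.** The shift is small beside sampling error, and the larger values need f = 10%.

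All of this limits the point's weight. None of it removes the asymmetry. The SAP 13 table is based on the Safety set, so it does not give f within mITT, and showing exclusions does not correct an estimate.

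The limits do rule out some stronger inferences. A reader might infer that the PP set screens adherence in the placebo arm alone, or that it keeps nearly all BCG recipients. The documents do not support that, because the other filters act in every arm. Nor can one say that a BCG participant with the same attendance always stays in. That turns on what the blinded data review classes as a major deviation, which the SAP leaves to other documents.

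**Conclusion.** The point holds in a limited form. The PP dose-completion criterion acts on placebo and, in practice, not on BCG, and nothing else in the plan offsets this for BCG versus placebo. The extra selection is confined to placebo participants who were Day 84-negative without a valid second dose.

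The shift in VE_PP is about +1 to -2 points at f = 3% and +3.5 to -7 points at f = 10%, for r from 0.5 to 2 and a true VE of 30%. All three quantities are assumed. The rule makes BCG look worse if placebo participants without the second dose convert faster than the rest, and better if they convert more slowly; the documents do not show which applies.

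A reader might take this as a threat to the primary BCG result or to the trial's power. It is neither: the mITT comparison and the sample size are untouched, and H4:IC31 versus placebo has the same rule in both arms. This is a cheap improvement to a sensitivity analysis.

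**What to change.** In SAP 5.5, and in the PP tables of SAP 14:

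- At the blinded data review, flag every blinded two-dose participant who is excluded from PP only for a Day 56 dose reason. The flag must cover both two-dose arms, because analysis sets are authorised before unblinding and placebo is masked against H4:IC31.
- Keep the current PP rule for H4:IC31 versus placebo.
- For BCG versus placebo, run the PP analysis with the flagged placebo participants retained, as a replacement or a supplement. Apply only exclusion criteria that can arise in both arms. The unintended-unblinding category in SAP 9, for example, does not apply to BCG.
- State in the tables that H4:IC31 versus BCG carries the same asymmetry.

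No new data are needed. The cost is one extra flag, a short wording change and a second placebo denominator in the PP tables.
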